## **CONFIDENTIAL PROTOCOL**

A Randomized, Double-Blind, Placebo-Controlled, Parallel-Design, Multiple-Site Clinical Study to Evaluate the Efficacy and Safety of Desoximetasone Topical Spray, 0.15% (Taro Pharmaceuticals, U.S.A., Inc.) in Patients with Mild to Moderate Plaque Psoriasis

---

## CONFIDENTIAL PROTOCOL

A Randomized, Double-Blind, Placebo-Controlled, Parallel-Design, Multiple-Site Clinical Study to Evaluate the Efficacy and Safety of Desoximetasone Topical Spray, 0.15% (Taro Pharmaceuticals, U.S.A., Inc.) in Patients with Mild to Moderate Plaque Psoriasis

---

### 4.0 SYNOPSIS

Protocol Number	71542603
Title	A Randomized, Double-Blind, Placebo-Controlled, Parallel-Design, Multiple-Site Clinical Study to Evaluate the Efficacy and Safety of Desoximetasone Topical Spray, 0.15% (Taro Pharmaceuticals, U.S.A., Inc.) in Patients with Mild to Moderate Plaque Psoriasis
Objectives	To evaluate the therapeutic efficacy and safety of desoximetasone topical spray, 0.15% (Taro Pharmaceuticals, U.S.A., Inc.) compared to a Placebo (vehicle) spray (Taro Pharmaceuticals, U.S.A., Inc.) in patients with mild to moderate plaque psoriasis
Sponsor	Taro Pharmaceuticals, U.S.A., Inc.
Study Products	

• Test: Desoximetasone topical spray, 0.15% (Taro Pharmaceuticals, U.S.A., Inc.)

• Placebo: Vehicle spray (Taro Pharmaceuticals, U.S.A., Inc.)

Route of Administration	Topical
Treatment Randomization	1:1 (Test: Placebo)
Patient Population	Up to 120 male and non-pregnant females, 12 years of age or older, with a confirmed diagnosis of mild to moderate plaque psoriasis will be enrolled to provide for up to 60 patients per each treatment group (Test or Placebo). Enrollment will begin with the 18 and older population. Enrollment for patients 12-17 will begin once we have safety data from the Phase 2 study has been reviewed.
Study Design	Randomized, double-blind, placebo-controlled, multiple-site, parallel design
Study Conduct	Eligible patients will be randomized in a 1:1 ratio to Test or Placebo product. Patients will complete 4 clinic visits over a 4 week study duration as follows: 

• Visit 1: Randomization (Day 1),

• Visit 2: Interim Visit (Day 7 ± 2),

• Visit 3: Interim Visit (Day 14 ± 2),

• Visit 4: End of Treatment (Day 28 ± 2).

 Patients will be contacted at Day 42 ± 4 (Visit 5) for a Telephone Follow-up to report any Adverse Events that have occurred since the end of treatment, Therapeutic efficacy evaluation will be based on clinical assessment of plaque psoriasis by the Investigator. Such clinical assessment will include scoring of the severity of signs and symptoms of plaque psoriasis. Refer to Appendices A, B and C for body surface area (BSA) estimation,

## CONFIDENTIAL PROTOCOL

A Randomized, Double-Blind, Placebo-Controlled, Parallel-Design, Multiple-Site Clinical Study to Evaluate the Efficacy and Safety of Desoximetasone Topical Spray, 0.15% (Taro Pharmaceuticals, U.S.A., Inc.) in Patients with Mild to Moderate Plaque Psoriasis

	Investigator's Global Assessment Scale (IGA), Total Lesion Severity Score (TLSS) and Psoriasis Area Severity Index (PASI), respectively.
Inclusion Criteria	

1. Male or non-pregnant, non-lactating female 12 years of age or older.

2. Signed informed consent form (ICF), which meets all criteria of current FDA regulations. For patients under the age of majority in the state the study is being conducted (18 years in most states) the parent or legal guardian should sign the consent form and the child will be required to sign a patient "assent" form that will be written in such a way as to be understandable to a child.

3. If female and of child-bearing potential, prepare to abstain from sexual intercourse or use a reliable method of contraception during the study (e.g., condom + spermicide, IUD, oral, transdermal, injected or implanted hormonal contraceptives).

4. Have a definite clinical diagnosis of stable plaque psoriasis involving 5-10% of the body surface area (BSA). Refer to Appendix A.

5. Have a plaque elevation score of <math>\geq 2</math> (mild) for the Target Lesion (based on TLSS, Appendix B).

6. The Target Lesion must have an area of at least 5 cm^2.

7. Have a Investigator's Global Assessment (IGA) score of 2 (mild) or 3 (moderate) at baseline for the overall disease severity (Appendix C).

8. Target Lesion must not be on the face, genitals, or intertriginous area (i.e., breast fold, gluteal crease, axilla, etc.).

Exclusion Criteria	

1. Patient is <math>< 12</math> years old.

2. Female who is pregnant, nursing, planning to become pregnant during the duration of the study, or if of child-bearing potential and sexually active and not prepared to use appropriate contraceptive methods to avoid pregnancy.

3. Has less than 5% or greater than 10% of BSA affected with plaque psoriasis.

4. A score of <math>< 2</math> (mild) for the individual sign of plaque elevation for the Target Lesion (based on TLSS, Appendix B).

5. Target Lesion area less than 5 cm^2.

6. Investigator's Global Assessment (IGA) Score <math>< 2</math> (mild) or <math>> 3</math> (moderate) at baseline for the overall disease severity.

## **CONFIDENTIAL PROTOCOL**

A Randomized, Double-Blind, Placebo-Controlled, Parallel-Design, Multiple-Site Clinical Study to Evaluate the Efficacy and Safety of Desoximetasone Topical Spray, 0.15% (Taro Pharmaceuticals, U.S.A., Inc.) in Patients with Mild to Moderate Plaque Psoriasis

---

	

7. Patient has current diagnosis of other types of psoriasis other than stable plaque psoriasis (i.e. acute, guttate, erythrodermic, exfoliative or pustular psoriasis) or has psoriasis of any kind of the face or scalp that will require active treatment during the study. Nonprescription antipsoriatic shampoos will be allowed during the study when applied solely to the scalp.

8. Patient presents active cutaneous bacterial or viral infection at baseline and/or skin atrophy in ant treatment area.

9. Patient has a history of psoriasis that has been unresponsive to topical corticosteroid therapy.

10. In the Investigator's opinion, the patient has other dermatological conditions, such as atopic or contact dermatitis, that may interfere with the clinical assessments of the signs and symptoms of psoriasis.

11. Patient has a history of allergy or sensitivity to corticosteroids or history of any drug hypersensitivity or intolerance which, in the opinion of the Investigator, would compromise the safety of the patient or the results of the study.

12. Patient has a significant history or current evidence of chronic infectious disease, system disorder, organ disorder or other medical condition that, in the Investigator's opinion, would place the study patient at undue risk by participation in the study.

13. Patient is currently receiving or has received any radiation therapy, anti-neoplastic agents or immunosuppressant medication within 4 weeks before the first dose of study drug.

14. Patient has undergone treatment with any systemic or photo antipsoriatic therapy within 8 weeks of the first dose of study drug.

15. Patient has been treated within 12 weeks (or five half lives, whichever is less) before the first dose of study drug with any biological therapies for psoriasis.

16. Patient has received any systemic steroids within 4 weeks of the first dose of the study drug. The use of inhaled or intranasal corticosteroids is acceptable as long as usage has been stable for at least 2 weeks before the first dose of study drug and will be continued during the study.

17. Females using hormonal contraceptives for less than one complete cycle before entering the study.

18. Patients who have used any topical anti-psoriatic agents of any kind or any topical corticosteroids for any reason within 2 weeks before first use of study drug. Nonprescription anti-psoriatic shampoos used only on the

--	--

## **CONFIDENTIAL PROTOCOL**

A Randomized, Double-Blind, Placebo-Controlled, Parallel-Design, Multiple-Site Clinical Study to Evaluate the Efficacy and Safety of Desoximetasone Topical Spray, 0.15% (Taro Pharmaceuticals, U.S.A., Inc.) in Patients with Mild to Moderate Plaque Psoriasis

---

	
scalp will be allowed during the study.
 
19. Receipt of any drug as part of a research study within 30 days before first dosing.
 
20. In the opinion of the Investigator, the patient will not be compliant with the requirements of the study procedures.
 
21. Previous participation in this study.

Efficacy Endpoints	
Primary Efficacy Endpoints
 

1. The proportion of patients in each treatment group who are considered a Clinical Success at Day <math>28 \pm 2</math> (i.e., at least a 2-grade improvement from the patient's baseline IGA score)

2. The proportion of patients in each treatment group who are considered a Treatment Success for the Target Lesion at Day <math>28 \pm 2</math> (i.e., a TLSS value of 0 or 1 at Day <math>28 \pm 2</math> for each of the three signs and symptoms (i.e., erythema, scaling and plaque elevation) depending on the patient's baseline TLSS)

 
Definitions:
 

1. Treatment Success: To be considered a Treatment Success the patient's TLSS value at Day <math>28 \pm 2</math> must be 0 if their baseline TLSS value is 2 and must be 0 or 1 if their baseline TLSS value is <math>> 2</math> for each of the individual signs and symptoms

2. Treatment Failure: A patient will be considered a Treatment Failure if:

a. the patient's TLSS value is <math>> 0</math> if their baseline TLSS value is 2 or <math>> 1</math> if their baseline IGA score is <math>> 2</math> for any of the individual signs and symptoms

b. the patient was considered to have an insufficient therapeutic response

3. Clinical Success: To be considered a Clinical Success the patient must have at least a 2-grade improvement from their baseline IGA score. That is, an IGA score of 0 at Day <math>28 \pm 2</math> if their baseline IGA score is 2 or an IGA score of 0 or 1 at Day <math>28 \pm 2</math> if their baseline IGA score is 3

4. Clinical Failure: A patient will be considered a Clinical Failure if:

a. the patient's IGA score is <math>> 0</math> if the baseline IGA score is 2 or <math>> 1</math> if the baseline IGA score is 3

b. the patient was considered to have an insufficient therapeutic response

## **CONFIDENTIAL PROTOCOL**

A Randomized, Double-Blind, Placebo-Controlled, Parallel-Design, Multiple-Site Clinical Study to Evaluate the Efficacy and Safety of Desoximetasone Topical Spray, 0.15% (Taro Pharmaceuticals, U.S.A., Inc.) in Patients with Mild to Moderate Plaque Psoriasis

---

	
Secondary Efficacy Endpoints
 
The secondary efficacy endpoints are:
 

1. The proportion of patients with a baseline IGA score of 3 who are considered a Clinical Success.

2. The proportion of patients with a baseline IGA score of 3 who are considered a Treatment Success.

3. The proportion of patients with a baseline IGA score of 2 who are considered a Clinical Success.

4. The proportion of patients with a baseline IGA score of 2 who are considered a Treatment Success.

5. The change from baseline in %BSA affected at Day 28 ± 2

Therapeutic Efficacy Analysis	
Primary Efficacy Analyses
 
The Test treatment will be compared with Placebo for each primary endpoint at the 5% significance level (<math>p < 0.05</math>; two-sided, Cochran-Mantel-Haenszel exact test) in the intent-to-treat (ITT) population using last observation carried forward (LOCF). As this is a multiple-site study, the interaction of treatment-by-site may be evaluated by the Breslow-Day test for homogeneity of the odds ratio at the 5% significance level (<math>p < 0.05</math>) for the primary efficacy variable in the ITT population for superiority testing. Superiority of Test over Placebo will be demonstrated if both dichotomous endpoints show statistical significance at the 5% significance level. For sensitivity testing, the primary analysis will also be performed using the per protocol (PP) population.
 
Secondary Efficacy Analyses
 
The Test treatment will be compared with Placebo for each dichotomous secondary endpoint at the 5% significance level (<math>p < 0.05</math>; two-sided, Cochran-Mantel-Haenszel exact test) in the ITT population using LOCF.
 
The Test treatment will be compared with Placebo for the continuous secondary endpoint at the 5% significance level in the ITT population using last observation carried forward (LOCF). Analysis of Covariance (ANCOVA) will be used for the evaluation of the continuous secondary endpoint using baseline %BSA as a covariate.
 
For the secondary efficacy analyses, superiority of Test over Placebo will be considered supported for each endpoint if the difference is statistically significantly greater than 0 at the 5% significance level. There will be no multiplicity adjustment for the evaluation of the five secondary endpoints.
 
Descriptive statistical analysis will be generated to compare the efficacy results in each treatment group at each visit.

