### 5.0 STUDY SCHEMATIC

PROCEDURE	VISIT 1 Randomization Day 1	VISIT 2 Interim Visit Day 7 ± 2 days	VISIT 3 Interim Visit Day 14 ± 2 days	VISIT 4 End of Treatment Day 28 ± 2 days	VISIT 5 Telephone Follow-Up Visit Day 42 ± 4 days
Informed Consent	X				
Medical History & Demographics	X				
Height and Weight	X				
Vital Signs	X	X	X	X	
Dermatological Assessment	X	X	X	X	
% BSA Assessment	X	X	X	X	
IGA Score	X	X	X	X	
Total Lesion Severity Score	X	X	X	X	
PASI Score	X	X	X	X	
Application Site Reactions	X	X	X	X	
Target Lesion Photograph**	X	X	X	X	
Pregnancy Test*	X			X	
Concomitant Medication	X	X	X	X	
Collect/Dispense Study Medication	X		X	X	
Provide/Review patient Dosing Diary	X	X	X	X	
Adverse Events		X	X	X	X
Evaluation of Patient Compliance to the Protocol		X	X	X	

\* Pregnancy Test will be conducted for women of child-bearing potential

\*\* Selected sites will be designated to take photographs of a defined target lesion at each Clinic Visit

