### 9.5.2 Visit 2 (Day 7 ± 2): Interim Visit

1. **Vital Signs:** The patient's vital signs will be recorded (pulse, blood pressure, temperature and respiration rate).
2. **Dermatological Assessment:** Clinical signs and symptoms of psoriasis will be evaluated by the Investigator based on the following:
  - % BSA assessment (Appendix A)
  - IGA Score (Appendix C)
  - TLSS Score (Appendix B)
  - PASI Score (Appendix D)
  - Application Site Reactions (Appendix E)
3. **Concomitant Medication:** Review the patient's use of any new or ongoing concomitant medications since Visit 1.
4. **Adverse Events:** Review and report any AEs since Visit 1.
5. **Diary Review:** Collect and review patient's dosing diary for compliance and provide new diary.
6. Schedule Visit 3.

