### **9.6.12 Dermatological Assessment**

At Visit 1 a visual inspection to confirm a diagnosis of chronic plaque psoriasis will be performed. At each visit psoriasis will be assessed according to the following measures:

- a) % BSA Assessment: Appendix A
- b) IGA Score: Appendix C
- c) TLSS: Appendix B
- d) PASI Score: Appendix D
- e) Application Site Reactions: Appendix E

Wherever possible, the same Investigator should attempt to perform all IGA exams at all visits for an individual patient.

During the overall dermatological assessment at Visit 1, the Investigator will determine which lesion in his opinion (considering a combination of size and severity of lesional signs and symptoms) is the most severe. This lesion must have an area of at least 5 cm^2 and have a plaque elevation score of at least 2 (mild).

This lesion will be designated the Target Lesion. If possible, the Target Lesion should exclude the elbows and knees. The location of the Target Lesion will be identified using an anatomical chart in the source documentation. The size of this lesion (cm^2) will be calculated, and the TLSS will be evaluated from this lesion.

To calculate the area of the Target Lesion the Investigator should measure once across its widest point and again at a point midway and perpendicular to the widest point. This should be done using the cm ruler provided. Measurements should be done to the nearest mm and reported in units of cm (i.e., reported as cm out to the first decimal place, not reported nor calculated in mm). These two values should be multiplied to give the total area of the Target Lesion (cm^2).

The Target Lesion should be used for all future evaluations and severity for individual signs and symptoms (scaling, erythema and plaque elevation).

To be eligible for inclusion at Visit 1, the patient must have all of the following:

- An affected BSA of 5 - 10% (Appendix A)
- A IGA score of 2 (mild) or 3 (moderate) (Appendix C)
- Target Lesion area of at least 5 cm^2
- Plaque Elevation Score  $\geq 2$  for the Target Lesion (based on TLSS score, Appendix B)

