### **10.7 Secondary Efficacy Analyses**

The Test treatment will be compared with Placebo for each dichotomous secondary endpoint at the 5% significance level ( $p < 0.05$ ; two-sided, Cochran-Mantel-Haenszel exact test) in the ITT population using LOCF.

The Test treatment will be compared with Placebo for the continuous secondary endpoint at the 5% significance level in the ITT population using LOCF. Analysis of Covariance (ANCOVA) with treatment and site as fixed effects and baseline %BSA as a covariate in the model will be used for the evaluation of the continuous secondary endpoint.

For the secondary efficacy analyses, superiority of Test over Placebo will be considered supported for each endpoint if the difference is statistically significantly greater than 0 at the 5% significance level. There will be no multiplicity adjustment for the evaluation of the five secondary endpoints.

Descriptive statistical analysis will be generated to compare the efficacy results in each treatment group at each visit.

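### Change in %BSA is tested at Day 28 by ANCOVA on carried-forward values although it is scored at Days 7, 14 and 28; depending on dropout, the estimate and the 5% test can be biased, and a repeated-measures model would use the data better

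*Protocol*

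**What the plan says.** Secondary endpoint 5 is "The change from baseline in %BSA affected at Day 28 ± 2" (Section 4.0 Synopsis; repeated in Section 10.5). It is the only continuous endpoint among those listed.

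The missing-data rule is fixed twice. The synopsis compares the arms "for the continuous secondary endpoint at the 5% significance level in the ITT population using last observation carried forward (LOCF"), and Section 10.7 does so "for the continuous secondary endpoint at the 5% significance level in the ITT population using LOCF". The model differs slightly between the two places. The synopsis says "Analysis of Covariance (ANCOVA) will be used for the evaluation of the continuous secondary endpoint using baseline %BSA as a covariate", while Section 10.7 specifies "Analysis of Covariance (ANCOVA) with treatment and site as fixed effects and baseline %BSA as a covariate in the model".

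The ITT population is all randomized subjects, and early leavers have their last observation carried forward (Section 10.3.1). Section 9.3.5 asks that leavers complete the Visit 4 procedures where possible.

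The intermediate data exist. The Section 5.0 schematic marks "BSA Assessment" at Visits 1 to 4, Sections 9.5.2 to 9.5.4 list it at Days 7, 14 and 28, and Section 9.6.12 introduces its list of measures with "At each visit psoriasis will be assessed according to the following measures".

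The only sensitivity analysis named is the per-protocol repeat of the primary analysis (Section 10.6). Section 10.1 leaves further missing-data procedures to the SAP, which is not at hand.

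**The concern.** LOCF-ANCOVA uses one change score per patient. A patient last seen at Day 7 or Day 14 enters with that visit's change, as though it had been measured at Day 28. If %BSA is still falling, that change is too small.

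The consequence depends on which arm loses patients and when. If an effect exists and dropout is equal, or heavier on Test, the difference shrinks. If there is no effect and one arm loses more patients, that arm's improvement is frozen early and a spurious difference appears. Section 10.7 lets superiority be called supported on this endpoint at an unadjusted 5%, so a distorted test can become a stated claim.

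Unequal dropout is conceivable. Section 9.3.4 lists both worsening signs or symptoms and possible HPA-axis suppression as reasons for removal, and these could plausibly fall on different arms.

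**Working it through.** **1. What the protocol supplies.** It gives no mean, SD, correlation or power for %BSA, and no dropout rate. Its 89% power belongs to the co-primary rates (40% v 12%, 50 per arm; a pooled Z-test gives 90.3%) and does not bear on this endpoint. The nearest figure is the enrolment allowance of 60 per arm for 50 evaluable: (60 − 50)/60 = 16.7%. That also covers patients who are otherwise non-evaluable, so it is an upper reading of dropout.

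**2. Formula.** Let a fraction *a* of an arm leave after Day 7 and *b* after Day 14, unrelated to outcome, with mean changes m7, m14 and m28. Then

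expected LOCF mean = (1 − a − b)·m28 + a·m7 + b·m14.

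**3. Assumed inputs (not in the protocol).** Mean change at Days 7/14/28 is −1/−2/−3.5 points on Test and −0.3/−0.6/−1 on vehicle. The true Day 28 difference is therefore −2.50. Leavers are split equally between *a* and *b*.

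**4. Worked case, 16.7% per arm (a = b = 1/12).**
- Test: (5/6)(−3.5) + (−1 − 2)/12 = −2.917 − 0.250 = −3.167
- Vehicle: (5/6)(−1) + (−0.3 − 0.6)/12 = −0.833 − 0.075 = −0.908
- Difference: −2.26, so the bias is +0.24, and 0.24/2.50 = about 10% toward zero.

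A simulation on these means (60 per arm, 2,000 runs, SD 1/1.5/2, correlation 0.7) also gave −2.26. The repeated-measures model gave −2.51.

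**5. Other patterns.** The last column is a separate simulation with different assumptions: SD 1.2/1.6/2.0, adjacent-visit correlation 0.7, true difference −1.7 to −2.5, dropout spread over all three intervals and either unrelated to outcome or missing at random.

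| Dropout Test / vehicle | LOCF difference by formula | Bias | Simulated LOCF bias |
|---|---|---|---|
| 5% / 5%, effect | −3.400 + 0.973 = −2.43 | +0.07 | +0.05 to +0.08 |
| 16.7% / 16.7%, effect | −2.26 | +0.24 | +0.19 to +0.29 (about 8-12%) |
| 25% / 8%, effect | −3.000 + 0.956 = −2.04 | +0.46 | +0.33 to +0.55 |
| 8% / 25%, effect | −3.340 + 0.863 = −2.48 | +0.02 | −0.06 to +0.06 |
| 8% / 25%, no effect, both on vehicle path | −0.956 + 0.863 = −0.09 | −0.09 | −0.12 to −0.15 (both arms improve 1 point) |
| 8% / 25%, no effect, both on Test path | −3.340 + 3.000 = −0.34 | −0.34 | −0.35 to −0.39 (both arms improve 3 points) |

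With a true effect, the repeated-measures model in the second simulation had bias within ±0.02 in every pattern.

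**6. False positives.** With no effect, the rejection rate is about P(|Z + bias/SE| > 1.96).
- Both arms improve 1 point: 0.12/0.35 = 0.34, giving Φ(−1.62) + Φ(−2.30) = 0.053 + 0.011 = 6.4%. Simulated: 6-7%.
- Both arms improve 3 points: 0.35/0.38 = 0.92, giving Φ(−1.04) + Φ(−2.88) = 0.149 + 0.002 = 15.1%. Simulated: 16-17%.

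The repeated-measures model rejected in 4-5% of runs in the same settings. With no effect and equal dropout, LOCF was unbiased.

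**7. Dependence on trajectory.** If both arms had reached their Day 28 level by Day 14, Day 14 leavers would add no bias. The bias in step 4 would fall to (1/12)(−0.7 + 2.5) = +0.15, or 6%.

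**The case against.** A reader might infer that the %BSA estimate is necessarily biased, or that LOCF always favours one arm. The documents do not support either. They state no trajectory and no dropout rate. At 5% dropout the bias is negligible, with equal dropout and no effect it is absent, and with a true effect and heavier vehicle dropout the errors nearly cancel. The 25% v 8% split is purely illustrative.

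A reader might also infer a broken confidence interval. LOCF coverage was indeed 88-92% at 16.7% dropout with a true effect, but the protocol promises a 5% test for this endpoint and no interval.

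With an effect of the assumed size, the decision hardly changes: −2.26/0.36 = 6.3 standard errors under LOCF against −2.51/0.39 = 6.4 under the alternative. %BSA is recorded to the nearest whole percentage, so a bias of 0.24 is about a quarter of one scoring unit. Nor are the earlier scores wholly unused, because descriptive results are promised at each visit.

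The early-termination assessment may supply a later value than the last scheduled visit, which the formula ignores. That softens the bias but does not remove it, since a value taken early is still carried to Day 28.

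Finally, the repeated-measures model relies on missing at random, and removal for worsening may not satisfy that. All of this stands and limits the size of the point. None of it is a reason to prefer LOCF when the three post-baseline scores are already collected.

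**Conclusion.** The concern holds in conditional form. The protocol itself fixes LOCF-ANCOVA for this endpoint, so this is a stated choice and not something left to the SAP. If %BSA is still changing after Day 7 or Day 14, the estimate and the 5% test can be biased, with direction and size governed by dropout. The sizes worked out above rest on assumed trajectories and SDs and on an upper reading of the 50-to-60 allowance.

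It would go too far to say that the trial's main conclusion is at risk. Superiority rests on the two dichotomous co-primary endpoints (Section 10.6), and this is one of five unadjusted secondary endpoints. Nor can it be said that no missing-data sensitivity analysis is planned, because the SAP is not available. What can be said is that this protocol names none for %BSA.

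**What to change.** In Section 10.7 and the synopsis, make the main %BSA analysis a mixed model for repeated measures on observed values at Visits 2, 3 and 4. Terms: treatment, visit, treatment-by-visit, site, baseline %BSA and baseline-by-visit, with unstructured covariance. Test the treatment difference at Day 28. Using the same model in both places also settles the site term, which Section 10.7 includes and the synopsis omits.

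Two handling rules are needed:
- Assign an early-termination Visit 4 assessment to the visit matching its actual study day, not to Day 28. State what happens to days outside the visit windows (2-4, 10-11 and 17-25 under the ±2-day windows) and to two values in one window.
- State how randomized patients with no post-baseline value are handled, since the ITT is all randomized subjects. One option is to put baseline %BSA in the response vector with a common mean across arms, in place of the baseline covariate terms.

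Keep LOCF-ANCOVA as a sensitivity analysis and add a missing-not-at-random check.

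The cost is wording and one standard model, with no new data. The main analysis then relies on missing at random, and the standard error is slightly larger: 0.39-0.41 against 0.35-0.39 in the simulations at 16.7% or unequal dropout.
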